2.1.2.2 Prohibited concomitant therapy

The following drugs are not permitted during the screening period and the treatment period:

- Any glucose-lowering agents other than the IMP, authorized background OADs and rescue therapy, if necessary,

Note: Short time uses (≤ 10 days) of short/rapid-acting insulin due to acute illness or surgery (eg, infectious disease) is allowed;

- Systemic glucocorticoids for more than 10 days (topical or inhaled applications are allowed),
- Body weight loss drugs.

After the last administration of IMP during the study period, any anti-diabetic treatments (other than GLP-1 receptor agonists) are permitted, as deemed necessary by the Investigator.

Any technical details related to computation, dates, imputation for missing dates are described in [Section 2.5](#).

2.1.3 Efficacy endpoints

All scheduled efficacy measurements collected during the study will be used in the analysis, including those obtained after IMP discontinuation or introduction of rescue therapy.

For sensitivity analyses, the 26-week on-treatment period is defined as follows:

- For patients who are not eligible to enter the extension period, the 26-week on-treatment period is defined as
 - For patients receiving daily IMP: the time from the first injection of open-label daily IMP up to 14 days for HbA1c; 0 day for standardized meal test parameters, 7-point SMPG and insulin glargine dose; 1 day for FPG; and 3 days for body weight after the last injection of IMP or up to the introduction of rescue therapy, whichever is the earliest.
 - For patients receiving weekly IMP: the time from the first injection of open-label weekly IMP up to 20 days for HbA1c; 6 days for standardized meal test parameters, 7-point SMPG; 7 days for FPG; and 9 days for body weight after the last injection of IMP or up to the introduction of rescue therapy, whichever is the earliest.
- For patients who are eligible to enter the extension period, the 26-week on-treatment period is defined as the time from the first injection of open-label IMP up to V28/Week 26 visit (or Day 183 if V28/Week 26 visit is missing), or up to the introduction of rescue therapy, whichever is the earliest.

The on-treatment period of the whole study including the 26-week single-arm FRC extension period for efficacy variables is defined as the time from the first injection of open-label IMP up to 14 days for HbA1c; 0 day for standardized meal test parameters, 7-point SMPG and insulin glargine dose; 1 day for FPG; and 3 days for body weight after the last injection of IMP or up to introduction of rescue therapy, whichever is the earliest.

The baseline value for efficacy endpoints is the last available value prior to the first injection of open-label IMP or the last available value on or before the date of randomization if not treated with open-label IMP.

HbA1c, FPG, and parameters from the 2-hour standardized meal test are measured in a central laboratory (see study flowchart in [Appendix D](#)).

Efficacy variables will be summarized in both standard international units and conventional units when applicable.

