7.2.5 Exclusion criteria for the extension period

- E 34. Patients in the FRC arm with a rescue therapy and HbA1c >8% at Week 22;
- E 35. Patients in the FRC arm who discontinued prematurely from FRC treatment before Week 26;
- E 36. Patients in the GLP-1RA treatment arm after randomization.

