8.1.3 Dose schedule

Insulin glargine/lixisenatide fixed ratio combination (FRC)

The FRC should be self-administered once daily in the morning in the hour (0 to 60 minutes) before breakfast, using Peach Pen or Olive Pen depending on the daily dose of insulin glargine.

Victoza®

Liraglutide (Victoza®) will be administered as per local labelling (such as SmPC in the European Union or PI in the US), continuing the same dose schedule as before randomization. Victoza® can be administered once daily at any time of day, independently of meals.

Byetta®

Exenatide BID (Byetta®) will be administered as per local labelling (such as SmPC in the European Union or PI in the US), continuing the same dose schedule as before randomization. Byetta® can be administered twice daily at any time within the 60 minute period before the morning and evening meal (or two main meals of the day, approximately 6 hours or more apart). Byetta® should not be administered after a meal.

At days of on-site visits, the IMP which is to be administered before breakfast should be self-administered at the investigational site under the observation of site staff.

Bydureon®

Exenatide extended-release (Bydureon®) will be administered as per local labelling (such as SmPC in the European Union or PI in the US), continuing the same dose schedule as before randomization. Bydureon® can be administered once a week at any time of day, independently of meals.

Tanzeum®

Albiglutide (Tanzeum®) will be administered as per local labelling (such as SmPC in the European Union or PI in the US), continuing the same dose schedule as before randomization. Tanzeum® can be administered once a week at any time of day, independently of meals.

Trulicity®

Dulaglutide (Trulicity®) will be administered as per local labelling (such as SmPC in the European Union or PI in the US), continuing the same dose schedule as before randomization. Trulicity® can be administered once a week at any time of day, independently of meals.

Injection site

The IMP should be administered by deep subcutaneous injection, alternating between the left and right anterolateral and left and right posterolateral abdominal wall or thighs or upper arms. Within a given area, location should be changed (rotated) at each time to prevent injection site skin reactions

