8.7.2 Return and/or destruction of treatments

Patients have to return all the used and in-use IMP (and corresponding leaflets if appropriate) at each on-site visit. Patients should also return the unused IMP each time a re-supply is planned (see [Section 1.2](#)).

Patients have to return all the used, in-use and unused IMP at V28 (or final assessment on treatment visit in case of permanent premature discontinuation).

All used, partially used or unused treatments will be retrieved by the Sponsor. A detailed treatment log of the returned IMP will be established with the Investigator (or the pharmacist) and countersigned by the Investigator and the Monitoring Team.

For NIMP not provided by the Sponsor, tracking and reconciliation will be managed according to local regulation.

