10.1 VISIT SCHEDULE

The visit schedule and procedures/assessments listed in the “Study Flow Chart” in [Section 1.2](#) are not repeated in this section. The aim of this section is to provide details on how some of the procedures/assessments have to be performed.

This is an outpatient study. The 26-week randomized period consists of 10 on-site visits, 8 titration phone calls (only for FRC arm) and 11 phone-call visits. Additional, optional phone call visits to monitor insulin glargine/lixisenatide combination dose adjustment should be scheduled whenever considered necessary by the Investigator.

During the single-arm extension period there will be 3 additional on-site visits and 4 phone call visits.

The patient has to be fasting for all on-site visits. For all these visits, the patient should be seen in the morning, at approximately the same time, as far as possible. The patient should take background OADs and inject the FRC or Victoza® or Byetta® (if injected in the morning) at the investigational site after the fasting blood sample has been drawn. Patients taking Bydureon®, Tanzeum®, or Trulicity® should follow their usual weekly injection schedule, and therefore do not necessarily need to inject at the investigational site on the day of an on-site visit.

The **fasting condition** is defined as an overnight fast no less than 8 hours that consisted of no food or liquid intake, other than water. IMP (not including the once weekly GLP-1 RAs) and other glucose-lowering agents should be administered after the fasting blood sample is drawn for all laboratory tests on the study site.

Note: If the patient is not fasting at the visits specified above, the blood sample will not be collected and a new appointment should be given to the patient for the following day if possible, with instruction to be fasted.

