For all continuous secondary endpoints, only descriptive statistics will be provided for the FRC group at the scheduled visits for the whole study period including the extension period. For all the categorical secondary endpoints defined for the extension period, counts and percentages will be summarized for FRC group using all data available at Week 52, with patients having data missing at Week 52 treatment as non-responders.

Sensitivity analysis

Sensitivity analyses will be performed for the following variables using scheduled measurements collected during the 26-week on-treatment period (excluding those collected after introduction of rescue therapy) (see [Section 2.1.3](#)). Continuous variables will be analyzed using MMRM or ANCOVA depending on the variables as specified earlier in [Section 2.4.4.2](#). Categorical variables will be analyzed using CMH method as described earlier. For the categorical variables in which HbA1c is assessed at Week 26, patients will be treated as failures (non-responders) if they have no assessment during the on-treatment period, including those who discontinue study treatment before Week 26, start rescue therapy before Week 26, or have no on-treatment assessment at all in mITT population.

- Change in 2-hour PPG and in glucose excursion during the standardized meal test from baseline to Week 26,
- Change in the daily average of the 7-point SMPG from baseline to Week 26 (each time point and average daily value),
- Change in FPG from baseline to Week 26,
- Change in body weight from baseline to Week 26,
- Percentage of patients reaching HbA1c $\leq 6.5\%$ at Week 26,
- Percentage of patients reaching HbA1c $< 7\%$ at Week 26.

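### The on-treatment window for the meal test drops some adherent control completers from the on-treatment PPG analysis because of when they inject; extension-eligible FRC completers are kept

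*SAP*

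**What the plan says.** SAP 2.1.3 defines the 26-week on-treatment period in two ways, and Protocol 9.2.1.1 does the same.

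- One definition opens "For patients who are not eligible to enter the extension period, the 26-week on-treatment period is defined as" and counts days from the last injection. For daily drugs the allowance is "0 day for standardized meal test parameters, 7-point SMPG and insulin glargine dose; 1 day for FPG", with longer allowances for body weight (3 days) and HbA1c (14 days). For weekly drugs the meal-test allowance is 6 days.
- Extension-eligible patients have a period that runs "up to V28/Week 26 visit (or Day 183 if V28/Week 26 visit is missing"), or to the start of rescue if that comes first. The date of the last injection plays no part.

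Protocol 7.2.5 bars from the extension "Patients in the GLP-1RA treatment arm after randomization", so every control patient comes under the first definition.

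On dosing and the visit:

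- Protocol 8.1.3: "Victoza® can be administered once daily at any time of day, independently of meals". Exenatide BID may be taken before two main meals that need not include breakfast.
- Protocol 9.2.1.2.2: the meal test is a fasting morning test. Injection at the site 30 minutes before the meal is required of FRC patients and of exenatide BID patients who dose before breakfast. Liraglutide is not named.
- Protocol 10.1: patients are to "inject the FRC or Victoza® or Byetta® (if injected in the morning) at the investigational site" once the fasting sample is drawn.
- Protocol 8.7.2: "Patients have to return all the used, in-use and unused IMP at V28".

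The window is used in SAP 2.4.4.2, whose on-treatment sensitivity analyses include "Change in 2-hour PPG and in glucose excursion during the standardized meal test from baseline to Week 26", and in the on-treatment C-peptide summary of SAP 2.4.4.4.

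**The concern.** An on-treatment analysis should separate patients still on drug from those who stopped or were rescued. Here the split among control completers depends on the hour of injection. A patient who took every dose, the last on the evening before V28, is tested the next morning and counted as off-treatment. A weekly patient tested 6 days after the last dose is counted as on-treatment. FPG from the evening injector's same visit is kept.

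SAP 2.4.4.2 notes that only one post-baseline meal test is scheduled. If that test is ruled out for a completer, LOCF has no other scheduled value to carry forward and the patient leaves the ANCOVA. The loss falls in one arm. The control group that remains is weighted towards patients dosed on the morning of the test and towards weekly users. This is the only sensitivity analysis the SAP plans for 2-hour PPG and excursion, the fourth step of the testing hierarchy.

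**Working it through.** The plan gives no figure for this point, so the check is date arithmetic on its rules, followed by an illustrative range.

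**Classification.** SAP Table 3 targets V28 at Day 183. A value is kept if Day 183 is no later than the end of the on-treatment period, where the end is the last injection day plus the allowance, or V28 itself for extension-eligible patients.

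| Completer without rescue | Last dose | Period ends (meal test) | V28 meal test |
|---|---|---|---|
| Control, liraglutide injected at site in the morning | Day 183 | 183 + 0 = 183 | kept |
| Control, liraglutide in the evening | Day 182 | 182 + 0 = 182 | dropped |
| Control, exenatide BID not taken before breakfast | Day 182 | 182 + 0 = 182 | dropped |
| Control, weekly drug, 1 to 6 days earlier | Day 177 to 182 | 183 to 188 | kept |
| Control, weekly drug, 7 days earlier | Day 176 | 176 + 6 = 182 | dropped |
| FRC, extension-eligible | Day 183 or 182 | V28 = 183 | kept |

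For the evening liraglutide patient, the other measurements at the same visit are kept: FPG (182 + 1 = 183), body weight (182 + 3 = 185) and HbA1c (182 + 14 = 196).

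**Why Day 182 is the last dose.** The pens go back at V28, and Protocol 8.8.3 leaves GLP-1 receptor agonists out of the treatments allowed after the last study dose. An evening user therefore has no dose later that day.

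**Why one arm only.** Under Protocol 7.2.5 an FRC patient is ineligible for the extension only by stopping FRC early, or by having both rescue therapy and HbA1c above 8% at Week 22. An FRC completer without rescue is therefore eligible, and the period runs to V28.

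**Size.** The documents give neither the share of control patients on liraglutide nor the share injecting in the evening. Take 250 control patients less the planned 20% drop-out: 250 × 0.80 = 200 completers. Then

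lost = 200 × (share on liraglutide) × (share of those injecting in the evening).

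- Low: 200 × 0.2 × 0.1 = 4 (2%)
- Middle: 200 × 0.4 × 0.3 = 24 (12%)
- High: 200 × 0.6 × 0.5 = 60 (30%)

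With 200 FRC completers and equal variances, the standard error of the difference is multiplied by √[(1/200 + 1/(200 − lost)) / (2/200)]: 1.005, 1.034 and 1.102 respectively. All the shares are assumptions. Exenatide BID and day-7 weekly cases are not counted.

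**The case against.** The strongest reply is that the last dose need not fall on the evening before V28. Protocol 10.1.2 has daily dosing continue up to V28, and Protocol 10.3.4 treats the V28 assessments as those of the last dosing day. In Protocol 10.1 the parenthesis about morning injection can be read as qualifying Byetta alone, so that every liraglutide patient injects at the site. The last injection date would then be V28 and a 0-day window would keep the test. SAP 2.5.3 takes that date from the eCRF, not from the return of pens.

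Part of this stands: the text is not fully explicit, and a site that had evening users inject at V28 would lose nothing. But the reading fits poorly with Protocol 8.1.3, which ties on-site injection to drug due before breakfast. It also fits poorly with Protocol 9.2.1.2.2, which leaves liraglutide out of the pre-meal instruction and makes the timing of the first blood draw conditional on a pre-breakfast dose. Nothing requires an evening user to inject before the test.

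A second reply is that 0 days is deliberate. Protocol 9.2.1.2.2 allows a meal test after discontinuation of a daily drug only if drug is received that day, and each variable has its own allowance. That is a good reason to keep the figure for patients who discontinue. It does not address completers.

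A third reply is that the reach is small: one supportive analysis and one descriptive table, with the full-data result reported beside them. That is correct and limits the weight of the point.

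**Conclusion.** The point holds, within limits. As written, the rule classes the V28 meal test of some adherent control completers as off-treatment because of injection time, and does not do so for extension-eligible FRC completers. It rests on reading 0 days by calendar date and on evening users not injecting before the test. Under the stated assumptions, evening liraglutide use would cost 4 to 60 of 200 control completers (2-30%), but the true number is unknown.

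Three stronger conclusions might be inferred, and the documents do not support them.

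- That the confirmatory result is compromised. SAP 2.4.4 and 2.4.4.2 analyse the primary endpoint and the fourth-step PPG and excursion test with all scheduled measurements, including those after discontinuation or rescue. Neither is affected.
- That a particular fraction of the control arm, such as a fifth of all 250, will be lost. Injection habits are not documented, and the relevant base is completers.
- That the sensitivity analysis is biased in a known direction or becomes uninformative. Neither a direction nor a size of bias can be derived; what can be shown is a selective loss and, in the illustration, a standard error 0.5-10% larger.

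It is worth correcting because a stated rule misclassifies patients and a short change removes the problem.

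**What to change.** In SAP 2.1.3 and Protocol 9.2.1.1, add a sentence stating that a V28 meal test in a patient who completed the 26-week randomized treatment without rescue is on-treatment for all meal-test parameters, in either arm. Extension-eligible FRC patients already have this rule. Keep the 0-day and 6-day windows for patients who stopped study drug early, where they agree with Protocol 9.2.1.2.2.

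Extending the daily window to 1 day, as for FPG, would be a weaker repair. It recovers evening injectors but leaves out the weekly user tested on day 7, and it relaxes the same-day condition for patients who discontinued.

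The cost is one added sentence in the definition and a completer flag in the programming. No new data are needed and no dosing or visit procedure changes. It should be settled before the 26-week database lock.

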2.1.3.1 Primary efficacy endpoint(s)

The primary efficacy endpoint is change in HbA1c (%) from baseline to Week 26.

2.1.3.2 Secondary efficacy endpoint(s)

Continuous secondary efficacy endpoints

The continuous secondary efficacy endpoints are:

- Change in FPG from baseline to Week 26,
- Change in 7-point SMPG profiles from baseline to Week 26 (each time point and average daily value),
- Change in 2-hour PPG and in blood glucose excursion during standardized meal test from baseline to Week 26,
- Change in body weight from baseline to Week 26,

7-point SMPG profiles will be analyzed based on the average of the glucose values recorded on eCRF on 2 different days in the week prior to the scheduled visits.

For 7-point SMPG profiles, the mean daily (ie, average on 7 points) change from baseline to Week 26 will be analyzed. In addition, the change from baseline to Week 26 for each of the 7 points will be evaluated, respectively.

For FPG, only values assessed in fasting condition will be analyzed.

Categorical secondary efficacy endpoints

The categorical secondary efficacy endpoints are:

- Percentage of patients reaching HbA1c $\leq 6.5\%$ (49 mmol/mol) at Week 26,
- Percentage of patients reaching HbA1c $< 7\%$ (53 mmol/mol) at Week 26.
- Percentage of patients requiring rescue therapy during the 26-week randomized treatment period.

2.1.3.3 Other endpoint(s)

- Insulin glargine and lixisenatide doses at Week 26 in the FRC group (for insulin absolute value and body weight adjusted);

- C-peptide evaluation during standardized meal test from baseline to Week 26;
- Percentage of patients reaching HbA_{1c} <7% (53 mmol/mol) with no body weight gain from baseline to Week 26.
- Percentage of patients reaching the fasting SMPG target (\leq 100 mg/dl) at Week 26 in the FRC group.
- Percentage of patients with no weight gain at Week 26.
- Pharmacokinetics parameters (FRC group): Total plasma concentrations of lixisenatide will be assessed in the time frame from 1 to 4 hours post-injection at Day 1 of the treatment phase and prior to injection as well as in the time frame from 1 to 4 hours post injection at Week 4, Week 12, Week 26.
- Insulin glargine doses will be analyzed based on the doses recorded on eCRF and lixisenatide doses will be derived based on the insulin glargine doses and pen information.
- An algorithm for defining patients requiring rescue therapy is provided in [Section 2.5.8](#).
- For the percentage of patients reaching HbA_{1c} <7% (53 mmol/mol) with no body weight gain at Week 26, “no weight gain” will be defined as negative change or no change from baseline to Week 26.

For further details on missing data handling, see [Section 2.5.3](#).

2.1.4 Safety endpoints

The safety endpoints are assessed by:

- Symptomatic hypoglycemia (documented, probable, severe symptomatic hypoglycemia),
- Adverse events (AEs), serious adverse events (SAEs), and AE of special interest (AESI),
- Safety laboratory values,
- Vital signs,
- Electrocardiogram (ECG).
- Immunogenicity (antibody variables, FRC group): anti-insulin and anti-lixisenatide antibodies.

Observation period

The observation period of safety data will be divided into 3 segments:

- The pre-treatment period is defined as the time between the date of the informed consent and the first injection of open-label IMP,
- The on-treatment period of the whole study for daily formulation is defined as the time from the first injection of open-label IMP up to 3 days (1 day for symptomatic hypoglycemia) after the last injection of IMP, regardless of the introduction of rescue

therapy. The on-treatment period of the whole study for weekly formulation is defined as the time from the first injection of open-label IMP up to 9 days (7 day for symptomatic hypoglycemia) after the last injection of IMP, regardless of the introduction of rescue therapy.

- The 26-week on-treatment period is defined as follows:
 - For patients who are not eligible to enter the extension period, the 26-week on-treatment period is defined as
 - For patients receiving daily IMP: time from the first injection of open-label daily IMP up to 3 days (1 day for symptomatic hypoglycemia) after the last injection of daily IMP, regardless of the introduction of rescue therapy.
 - For patients receiving weekly IMP: time from the first injection of open-label weekly IMP up to 9 days (7 day for symptomatic hypoglycemia) after the last injection of weekly IMP, regardless of the introduction of rescue therapy.
 - For the patients who are eligible to enter the extension period, the 26-week on-treatment period is defined as the time from the first injection of open-label IMP up to V28/Week 26 visit (or Day 183 if V28/Week 26 visit is missing).
- The post-treatment period is defined as the time starting 4 days (2 days for symptomatic hypoglycemia) after the last injection of open-label daily IMP, or starting 10 days (8 days for symptomatic hypoglycemia) after the last injection of open-label weekly IMP (after the on-treatment period of the whole study).

The on-study observation period is defined as the time from the first injection of open-label IMP until the end of study (defined as last protocol planned visit or the resolution/stabilization of all serious AEs and AEs with pre-specified monitoring as defined in the protocol).

The baseline value for safety endpoints will be the last available value prior to the first injection of open-label IMP.

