--	---

	
 • Patient who has a renal function impairment with estimated glomerular filtration rate (GFR) <30 mL/min/1.73 m² (using MDRD formula) or end-stage renal disease; • Contraindication to use of insulin glargine, or lixisenatide or GLP-1 receptor agonist (Victoza®, Byetta®, Bydureon®, Tanzeum®/ or Trulicity®) according to local labeling; • Any contraindication to metformin or pioglitazone or SGLT2 inhibitors (when applicable) use, according to local labeling; • History of hypersensitivity to insulin glargine, or to any of the excipients; • History of allergic reaction to any GLP-1 receptor agonist or to Metacresol; • Personal or immediate family history of medullary thyroid cancer (MTC) or genetic condition that predisposes to MTC (eg, multiple endocrine neoplasia type 2 syndromes); • History of pancreatitis (unless pancreatitis was related to gallstones and cholecystectomy was already performed), chronic pancreatitis, pancreatitis during a previous treatment with incretin therapies, pancreatectomy; • Body Mass Index (BMI) ≤20 or >40 kg/m².

Main selection criteria for the extension period
	
Inclusion criteria:
 
 • Patients treated with FRC during the 26-week randomized treatment period. 
Exclusion criteria:
 
 • Patients in the FRC arm receiving rescue therapy and HbA1c >8% at Week 22; • Patients in the FRC arm who discontinued prematurely from FRC treatment before Week 26; • Patients in the GLP-1RA treatment arm after randomization.

Total expected number of patients
	
Approximately 500 patients randomized in the study (250 patients per group) during the open-label randomized treatment period.
 
Approximately 230 patients are estimated to enter the single-arm extension period with the treatment of FRC.

STUDY TREATMENT(s)	

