6 STUDY DESIGN

6.1 DESCRIPTION OF THE PROTOCOL

The study will be an open label, randomized, active-controlled, 2 treatment-arm, 26-week treatment duration, parallel-group, multinational and multicenter phase 3 study comparing the FRC to GLP-1 receptor agonist. At the end of the 26-week randomized period, patients from the FRC group will be invited to participate in a 26-week single arm extension. The study will recruit outpatients with T2DM. At the end of the screening period, eligible patients will be randomized to one of two treatment groups:

- FRC group;
- GLP-1 receptor agonist group.

The randomization (1:1) will be stratified by values of HbA1c at screening (<8%, ≥8%) (<64 mmol/mol, ≥64 mmol/mol) and GLP-1 receptor agonist subtype (once/twice daily formulations, once weekly formulations).

The study will comprise 4 periods:

1. An up-to 2-week screening period;

- Eligible patients continue their GLP-1 RA (Victoza®, Byetta®, Bydureon®, Tanzeum®, or Trulicity®) on top of metformin ± pioglitazone ± SGLT2 inhibitors at the same doses/dose regimens as before the screening visit.

2. A 26-week open-label randomized treatment period;

- Eligible patients will be randomized at V3 to either receive the FRC on top of metformin ± pioglitazone ± SGLT2 inhibitors or to continue on GLP-1 receptor agonist on top of metformin ± pioglitazone ± SGLT2 inhibitors.

3. A 26-week single-arm extension period

- For patients treated with the FRC during the randomized period;
After the end of the randomized treatment period (Week 26) patients will continue to use the FRC during the next 26 weeks of the extension period. Patients on rescue therapy during the randomized period and still having their HbA1c >8% at Week 22 and the patient who discontinued prematurely from treatment before Week 26 will not be invited to participate in the extension period.
- For patients treated with GLP1-RA during the randomized period.
Patients will not be invited to participate in the extension period and will be prescribed the most appropriate antidiabetic treatment at the Investigator's discretion.

4. A post-treatment follow-up period:

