9.2.2 Safety endpoints

The safety endpoints are assessed by:

- Symptomatic hypoglycemia (documented, probable, severe symptomatic hypoglycemia);
- Adverse events (AE), serious adverse events (SAE); adverse event of special interest (AESI), AEs requiring specific monitoring and reporting on specific electronic case report forms (e-CRFs) (suspected allergic reactions, patients with increased pancreatic enzymes >2 ULN/pancreatic events, patients with increased calcitonin ≥ 20 pg/mL, Device-related events (DRE));
- Safety laboratory values;
- Vital signs;
- Electrocardiogram (ECG);
- Immunogenicity (antibody variables, FRC group): anti-insulin and anti-lixisenatide antibodies.

Observation period of safety endpoints

The observation period of safety data will be divided into 3 segments:

- The pre-treatment period is defined as the time between the date of the informed consent and the first injection of open-label IMP;
- The 26-week on-treatment period is defined as follows:
 - For patients who are not eligible to enter the extension period, the 26-week on-treatment period is defined as:
 - For patients receiving daily IMP: time from the first injection of open-label daily IMP up to 3 days (1 day for symptomatic hypoglycemia) after the last injection of daily IMP, regardless of the introduction of rescue therapy;
 - For patients receiving weekly IMP: from the first injection of open-label weekly IMP up to 9 days (7 day for symptomatic hypoglycemia) after the last injection of weekly IMP, regardless of the introduction of rescue therapy.
 - For the patients who are eligible to enter the extension period, on-treatment period is defined as time from the first injection of open-label IMP up to V28/Week 26 visit (or Day 183 if V28/Week 26 visit is missing).
- The on-treatment period for the whole study (including the 26-week extension period) is defined as the time from the first injection of open-label IMP up to 3 days (1 day for symptomatic hypoglycemia) after the last injection of IMP, regardless of the introduction of rescue therapy. For patients who are not eligible to enter the extension period, the on-treatment period for the whole study is the 26-week on-treatment period.

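### The 26-week safety window ends at Week 26 for extension-eligible FRC patients but runs a few days longer for every control completer, so unadjusted event percentages carry a small one-way bias

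*SAP*

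**What the plan says.** SAP 2.1.4 (Observation period) and Protocol 9.2.2 define the 26-week on-treatment period for safety in two ways.

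- **Eligible for the extension:** the period is "the time from the first injection of open-label IMP up to V28/Week 26 visit (or Day 183 if V28/Week 26 visit is missing". There is no tail after the last injection. Protocol 9.2.2 has the same rule: "For the patients who are eligible to enter the extension period, on-treatment period is defined as time from the first injection".
- **Not eligible, daily product:** "up to 3 days (1 day for symptomatic hypoglycemia) after the last injection of daily IMP".
- **Not eligible, weekly product:** "up to 9 days (7 day for symptomatic hypoglycemia) after the last injection of weekly IMP, regardless of the introduction of rescue therapy".

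Eligibility is tied to arm. Exclusion E 36 in Protocol 7.2.5 bars "Patients in the GLP-1RA treatment arm after randomization". An FRC patient who completes 26 weeks is eligible unless E 34 applies (rescue therapy with HbA1c above 8% at Week 22). The Protocol synopsis states: "Approximately 230 patients are estimated to enter the single-arm extension period with the treatment of FRC".

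After Week 26, control patients "will be prescribed the most appropriate antidiabetic treatment at the" Investigator's discretion (Protocol 6.1). Protocol 8.8.3 allows any antidiabetic drug other than a GLP-1 receptor agonist once study drug has ended.

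SAP 2.4.5 applies these periods to the classification of adverse events, and SAP 2.4.5.1 applies them to hypoglycaemia. SAP 2.4.5.2 takes adverse-event percentages over the safety population of each group.

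**The concern.** The 26-week safety tables are the only randomized safety comparison in the trial. Their follow-up should not differ by arm for reasons built into the definition. Here, for two patients who both took study drug to Week 26, the end of the window is set almost entirely by the arm: V28 for the FRC patient, and some days after V28 for the control patient.

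The extra days can only add events to the control column, so FRC looks slightly safer by comparison. The added days also fall when control patients may be changing treatment. The window has no cut at the start of new therapy, so an event after a switch would be labelled as on-treatment with the GLP-1 receptor agonist. Control completers have a follow-up contact in those days that asks about hypoglycaemia and new medication (Protocol 10.1.2.6). FRC patients who continue have no such contact then.

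**Working it through.** **The plan's own figure.** With the first injection on Day 1, Week 26 is Day 26 × 7 + 1 = 183. This matches the Day 183 in SAP 2.1.4.

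**Window end for a completer with V28 on Day 183.** End day = last injection day + tail. Excess = end day − 183, and percentage = excess / 183.

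| Patient | Last injection | AE window end | AE excess | Hypoglycaemia window end | Hypoglycaemia excess |
|---|---|---|---|---|---|
| FRC, eligible | continues | 183 | 0 | 183 | 0 |
| Control, daily | V28 day | 186 | 3 (1.6%) | 184 | 1 (0.5%) |
| Control, weekly | V28 day | 192 | 9 (4.9%) | 190 | 7 (3.8%) |
| Control, weekly | 1 day before | 191 | 8 (4.4%) | 189 | 6 (3.3%) |
| Control, weekly | 3 days before | 189 | 6 (3.3%) | 187 | 4 (2.2%) |
| Control, weekly | 6 days before | 186 | 3 (1.6%) | 184 | 1 (0.5%) |

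Protocol 9.2.1.2.2 prefers the meal test one to three days after the weekly injection. A weekly control completer who follows that preference gains 6 to 8 days for adverse events and 4 to 6 days for hypoglycaemia.

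**How many FRC patients are cut at Week 26.** By the synopsis estimate, 230/250 = 92%. If the 20% drop-out in the sample-size section is used instead, 200/250 = 80%.

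**Average control excess.** The documents give no daily/weekly split. Assuming a weekly share w of 25% to 75%, the largest average excess for adverse events is 9w + 3(1 − w). That gives 4.5 to 7.5 days, or 2.5% to 4.1% of 183.

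**Effect on a percentage.** Assume a constant hazard and an incidence p over 183 days. With k extra days it becomes 1 − (1 − p)^((183 + k)/183).

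- p = 10.0%: 10.2% at k = 3 and 10.5% at k = 9.
- p = 50.0%: 50.6% at k = 3 and 51.7% at k = 9.

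**What is adjusted.** SAP 2.4.5.1 computes hypoglycaemia rates over treatment duration plus 1 day (daily) or 7 days (weekly), so the control tail is in that denominator. An eligible FRC patient also gets the extra day although the events counted stop at V28. Adverse-event percentages, and the number (%) of patients with hypoglycaemia, have no such adjustment.

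**The case against.** The strongest reply is that the tail is deliberate. Both documents define treatment-emergent events as those up to 3 days, or 9 days for a weekly product, after the last dose. Seven of the nine weekly days match the dosing interval that SAP 2.4.3.1 counts as exposure. FRC is cut at V28 because dosing continues. The safety analyses are descriptive with no testing (SAP 2.4.5), and the tables by weekly interval for documented hypoglycaemia and for nausea and vomiting stop at 26 weeks. All of this stands and limits the size. It does not make the windows equal in the main percentage tables.

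The documents do not support four stronger readings that a reader might infer.

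- *All controls gain nine days.* Nine is the maximum, for adverse events only and for weekly products only, when the last injection is on the V28 day.
- *Hypoglycaemia from new insulin will be charged to control.* The protocol permits new therapy but does not say when it starts or that it is insulin. SAP 2.4.5.1 also repeats the hypoglycaemia summary for the period before rescue. Whether a switch after V28 would count as rescue depends on SAP Appendix B, which is not in the text available.
- *FRC events after V28 are lost.* They appear in the FRC whole-study tables.
- *An eligible FRC patient who declines the extension certainly gets no tail.* SAP 2.1.4 splits by eligibility, but SAP 2.5.3 sets the last-injection date for the same window by participation. The text is ambiguous.

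**Conclusion.** The window depends on arm as written, and the direction is fixed: among completers it adds control events and none for eligible FRC patients. The size is small, at most 1.6% more time at risk for daily controls and 4.9% for weekly controls (adverse events), or 0.5% and 3.8% for hypoglycaemia. Under a constant hazard that is 1.7 percentage points at most on a 50% incidence. These figures assume V28 on Day 183. A constant hazard does not describe a change of therapy, so any effect of new treatment in those days would come on top and cannot be sized from the documents.

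The point is limited to completers. Early discontinuers in both arms, and FRC completers barred by E 34, keep a tail. It would be wrong to infer that a hypothesis test or the primary conclusion is affected. The change is still worth making, because it is cheap and removes an arm-dependent rule from the only randomized safety comparison.

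**What to change.** For the between-group 26-week tables of adverse events and hypoglycaemia, end the window at V28 (Day 183 if missing) for every patient in either arm still on study drug at V28. Keep the 3- or 9-day tail (1 or 7 days for hypoglycaemia) only for patients who stopped earlier.

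Four conforming edits are needed, or the change creates new problems.

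1. In SAP 2.4.5.1, use the same truncated time as the exposure denominator for these tables. If the added 1 or 7 days stayed, control hypoglycaemia rates would be diluted.
2. Leave the treatment-emergent definitions (Protocol 11.4.6.2, SAP 2.1.4.2) and the reach of the whole-study period as they are. Protocol 9.2.2 sets the whole-study period of ineligible patients equal to their 26-week period. That sentence must state the tail directly, or control events just after V28 would fall in no defined period.
3. Show treatment-emergent events after V28 in the residual period separately by arm.
4. Use one term, eligible or participating, in SAP 2.1.4 and 2.5.3.

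The minimum alternative is to keep the current tables and add adverse-event and hypoglycaemia tables truncated at V28/Day 183 in both arms.

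The cost is SAP and protocol wording plus some table programming, with no new data. The downside is that a few control events from residual exposure move to a separate display.
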